- The proportion of subjects who lose at least 5% of baseline truncal body fat in the active versus placebo treated groups. (As measured by a whole body DXA scan).
- The difference in mean percent loss of baseline visceral adipose tissue in the active versus placebo treated groups. (As measured by a whole body DXA scan).
- The proportion of subjects who lose at least 5% of baseline visceral adipose tissue in the active versus placebo treated groups. (As measured by a whole body DXA scan).

- Difference in lean muscle mass in the active versus placebo treated group. (As also automatically measured by the whole body DXA scan).
- Difference in bone mineral content in the active versus placebo treated group. (As also automatically measured by the whole body DXA scan).
- Blood pressure
- Heart rate
- Lipid profile (Assess total non-HDL cholesterol, and HDL to total cholesterol ratio)
- High-sensitivity C-reactive protein
- Oral glucose tolerance test (See Appendix 5)
- Fasting insulin level
- Waist and hip circumferences
- Body Mass Index (BMI)
- Adjustment of concomitant medication – both reduction and new medications
- Quality of life – IWQOL-Lite questionnaire. This validated instrument, developed by Duke University, has been used by a variety of researchers to assess various obesity treatment options and their impact on individual patients. The questionnaire is available in a number of languages including Spanish. A detailed description is available on this website: <https://olv.duke.edu/iwqol>. As can be seen on this website this instrument has been used extensively in studies relating to weight loss and obesity: <http://www.qualityoflifeconsulting.com/iwqol-litepublications.html>.
- Dose response analysis: it is likely that some subjects will not utilize their device for the mandated 5 hours per week. Usage data will be available from the devices as they can distinguish when they are genuinely being used as opposed to just being turned on with air between the electrodes. Data from such subjects will be analyzed in the main study but if possible a dose response analysis will also be carried out. Analysis will be in an intention to treat manner – see Statistical Considerations.

Safety Endpoints and Adverse Event Monitoring

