Data will be transferred in an encrypted PDF format. Trial staff will be given direction on how to share the trial data and given access to one specific section of a controlled cloud service which is controlled via role based access. Once they have authenticated with the service and the service verifies that they have the correct role to access the system they will be directed to a single webpage within the application where they will be able to upload the encrypted PDF. This PDF is generated on the fly and is therefore not stored in another location that could become compromised. Generating the PDF on the fly means that the source data is extracted from the database, processed and delivered in the context of a single request. This is an important factor as this means that after the request finishes the data in the PDF will not be held in application memory once the request is finished and the data relating to the request is freed. After the PDF is generated it is delivered to the assigned statistician using TLS 1.2 (a strong protocol), ECDHE_ECDSA with X25519 (a strong key exchange), and AES_128_GCM (a strong cipher). These data will be transferred for each subject when they complete participation in the study. If they complete the study protocol this will be at the one-year mark, however, if they drop out early then data accrued up until that point will be sent.

References

STATISTICAL CONSIDERATIONS

These statistical considerations were constructed in conjunction with [name] of the bio-statistics unit at the ACTRI.

Randomization

Treatment assignments will be generated via a randomized block procedure, with block sizes randomly chosen in the set {2, 4, 6, 8, 10, 12}. Subjects will be assigned 2:1 between treatment and control groups. Stratification will be performed by gender and center.

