Methods: Primary Aims

For total body weight loss (TBWL) as a continuous measure, we will use a two-sample t-test to examine the differences between the control and active treatment groups at each time period. We will also build one-sided confidence intervals to test whether the difference between groups exceeds a superiority margin of 5%. As a secondary analysis, we will also use a linear regression with TBWL as the dependent variable and group and other covariates of interest (gender, age, etc.) as independent variables. To assess any longitudinal effects, we will use a linear mixed effects model for weight over time, with fixed covariates for baseline weight, time, group, and a time / group interaction, and a random intercept to account for within-subject correlation. We will use a one-sided exact binomial test to determine if the response rate in the treatment group significantly exceeds 35%, with response defined by a loss of at least 5% of their body weight at the 12-month follow-up. We will also use Fisher's exact test to compare the response rates in each group, and, as a secondary analysis, will consider the use of a logistic regression to control for any other covariates of interest. To investigate possible longitudinal trends, we will fit a logistic mixed effects model, similar to the linear mixed effects model described above.

Methods: Secondary Aims

For each continuous and categorical variable at each time point, we will use a two-sample t-test and Fisher's exact test, respectively. Summary statistics (mean, standard deviation, quantiles, counts, and percentages) and plots will be produced for all demographic and study outcomes. We will investigate the effectiveness of the device by usage by including usage time as a continuous covariate in a linear model for TBWL. CTRI Biostatistics Core personnel will conduct all analyses using the latest version of R (R Foundation for Statistical Computing, Vienna, Austria. <http://www.R-project.org/>). No alpha spending function is applied to adjust for multiple comparisons across the secondary aims, and no claims will be made based on any of the secondary endpoints, which are instead viewed as hypothesis generating endpoints.

Missing Data

The primary hypotheses will be tested on the intent-to-treat population. A sensitivity analysis will be

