performed with the binary weight loss endpoint. This analysis will include a best-case scenario (assuming subjects with missing values have all lost over 5% body weight), a worst-case scenario (assuming no subjects with missing values have lost over 5% body weight), and a tipping point analysis (as described in Yan¹). We will check the assumption that the data is missing completely at random, and use multiple imputation techniques to reduce bias in the estimation of the treatment effect. Missing data will be clearly reported and included in tables.

Power Calculation

The primary outcomes are TBWL from the start of treatment until the 12-month mark and the number of subjects who lose at least 5% of their baseline total body weight. We will power both of these tests at the 0.025 significance level (a Bonferroni correction to maintain a family-wise error rate of 0.05 in our primary analysis). For TBWL, we will test the following null and alternative hypothesis:

$$\begin{aligned} H_0: \mu_t - \mu_c &\leq 5\% \\ H_1: \mu_t - \mu_c &> 5\% \end{aligned}$$

where μ_t and μ_c are the treatment and control mean TBWL in the ITT population. We will use a one-sided two-sample t-test to determine if there is a statistically significant difference in TBWL between our control and treatment arms beyond a superiority margin of 5%. With a total sample size of 90 subjects (30 sham and 60 active treatment), this t-test will have 80% power at the $\alpha = 0.025$ significance level to detect an effect size of $d = 0.63$. Assuming a similar standard deviation of TBWL as the ReShape trial (7.5%), this translates to a detectable difference in TBWL between the treatment and control groups of 4.75%. Assuming this same standard deviation, a two-sample superiority test will have 80% power assuming that the true difference between groups is 6.33%.

For the proportion of treatment subjects who lose at least 5% of their baseline total body weight, we will test the following null and alternative hypothesis:

$$\begin{aligned} H_0: P_t &\leq 35\% \\ H_1: P_t &> 35\% \end{aligned}$$

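### hs-CRP and fasting insulin are to be compared by an unadjusted, untransformed t-test; if they are strongly skewed, this gives up power that log values adjusted for log baseline would keep

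*Combined protocol and SAP*

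**What the plan says.** Section 9, Methods: Secondary Aims, gives a single instruction: "For each continuous and categorical variable at each time point, we will use a two-sample t-test" (with Fisher's exact test for the categorical ones). The list of 12-month secondary outcomes includes "High-sensitivity C-reactive protein" and "Fasting insulin level", and both are also measured at site visit 1, so a baseline value exists.

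No log transformation, geometric mean, rank test or normality check is mentioned for these markers. Quantiles and plots are promised for all outcomes, but no analysis decision depends on them. The plan does not say whether the follow-up value or the change is tested, or whether the t-test assumes equal variances. It names R as the software, and R's standard t-test function uses the Welch form unless told otherwise.

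On allocation: "Subjects will be assigned 2:1 between treatment and control groups". The same section treats the secondary endpoints as hypothesis generating and rules out claims from them.

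**The concern.** Positive laboratory markers often have a long right tail. If these do, a few high readings dominate the arm means and inflate the standard error, and the small sham arm is the most exposed. Device effects on such markers are also more naturally proportional than additive. An analysis of untransformed values can then miss a signal that the same data would show on the log scale. Leaving the scale and the form of the t-test open also invites a choice after the data are seen.

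Only the sensitivity of an exploratory comparison is at stake. The primary weight-loss analyses and the sample size are untouched.

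**Working it through.** **Inputs from the plan.** 60 active and 30 sham evaluable subjects (Power Calculation).

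**Assumptions, because the documents are silent.** Two-sided 0.05 for the secondary tests; lognormal values with the same log-SD in both arms; log-SD 0.6 to 1.2; follow-up values tested. The effect is a geometric mean ratio (active/sham).

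**The plan's own t-test figure.** Power Calculation: "With a total sample size of 90 subjects (30 sham and 60 active treatment), this t-test will have 80% power" (one-sided 0.025, d = 0.63). The noncentral t gives 79.6%. Exactly 80% needs d = 0.633, and 0.633 × 7.5% = 4.75%, as stated. The figure reproduces. No power is stated for hs-CRP or insulin.

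**Log-scale t-test.** d = |ln(ratio)| / log-SD, with noncentrality d × √(30 × 60 / 90) = 4.47 d.
- Log-SD 0.6, ratio 0.7: d = 0.357 / 0.6 = 0.594, power 75%.
- Log-SD 1.0, ratio 0.6: d = 0.511 / 1.0 = 0.511, power 62%.
- Log-SD 1.2, ratio 0.5: d = 0.693 / 1.2 = 0.578, power 72%.

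**Untransformed t-test, by simulation (40,000 trials per setting).**

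| Log-SD | Ratio | Pooled | Welch | Log values | Loss, pooled | Loss, Welch |
|---|---|---|---|---|---|---|
| 0.6 | 0.7 | 70% | 63% | 75% | 5 | 12 |
| 1.0 | 0.6 | 50% | 35% | 62% | 12 | 27 |
| 1.2 | 0.5 | 55% | 35% | 72% | 17 | 37 |

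These are three paired settings, not every combination of the two ranges. At log-SD 0.6 and ratio 0.5, for example, all three tests have power above 99% and the loss is under half a point.

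**Smaller effects.** At ratio 0.8, pooled against log power is 35% / 38%, 15% / 17% and 11% / 13% for log-SD 0.6, 1.0 and 1.2. That is a loss of about 2 points; Welch loses 8 to 10. At ratio 0.9 the pooled loss is under 1 point.

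**Why the form of the t-test matters.** A lognormal SD equals its mean × √(exp(log-SD²) − 1). At log-SD 1.0 the factor is √1.718 = 1.311. Set the sham mean to 1.
- Ratio 0.6: variances are 1.718 (sham) and 0.36 × 1.718 = 0.618 (active); the difference is 0.4. Welch SE = √(1.718/30 + 0.618/60) = 0.260, so difference/SE = 1.54. Pooled variance = (29 × 1.718 + 59 × 0.618)/88 = 0.981, SE = √(0.981 × 0.05) = 0.221, so difference/SE = 1.81. On logs it is 4.47 × 0.511 = 2.28.
- Ratio 1.67: the active variance is 1.718/0.36 = 4.772; the difference is 0.667. Welch SE = 0.370, giving 1.80. Pooled variance = 3.765, SE = 0.434, giving 1.54.

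The ranking of the two forms reverses with the direction of effect. Simulation agrees: at log-SD 1.0 and ratio 1.67, power is 38% pooled, 54% Welch and 62% on logs.

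**No effect.** Rejection rates are about 4% to 5% for the pooled test and about 5% for Welch and for logs.

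**Log value adjusted for log baseline.** With an assumed log-scale baseline correlation of 0.6, the residual SD shrinks by √(1 − 0.36) = 0.8, so d becomes 0.743, 0.639 and 0.722. Simulated power is about 90%, 81% and 89% in the three settings, in table order.

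**The case against.** The strongest reply is that the documents do not establish a problem. They give no SD, skewness or expected effect for either marker, and right skew is general knowledge rather than a fact of this protocol. That the values are untransformed is itself inferred from the plan's silence. The table's effects are large for a trial seeking a weight difference of about 5% to 6%; for modest effects no test has useful power and the pooled loss nearly vanishes. Type I error is kept, no claims rest on these endpoints, and the promised plots and quantiles would make skew visible. All of this stands, and it limits the point to a minor improvement.

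Several stronger readings are not supported:
- A reader might infer that the plan costs about 18 points of power for both markers. A loss of that size needs a log-SD near 1.2 and a roughly halved geometric mean. It is not a ceiling either: at log-SD 1.3, with an effect giving 80% power on logs, the pooled loss is about 21 points. At log-SD 0.5 to 0.7, a range one might assume for insulin, the pooled loss with that same 80%-power effect is only about 3 to 6.5 points.
- A reader might infer that R's default is always the worse choice. That holds only if the device lowers the marker.
- A reader might extend the point to visceral adipose tissue. The plan already defines that outcome as percent loss from baseline, a proportional scale that can be negative, and adds a responder proportion.
- Nothing in the documents makes these markers the main place to look for a signal. The secondary list opens with DXA fat outcomes, and the pilot finding concerned truncal fat.

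What the reply does not remove is that a better analysis is available from data already collected, and that it does better in either direction of effect.

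**Conclusion.** The point holds as a low-impact improvement. The only between-group test specified for hs-CRP and fasting insulin is an unadjusted t-test with no transformation and no stated variance form. Under lognormality, in the three settings with log-SD 0.6 to 1.2 and geometric means 30% to 50% lower on active, it loses about 5 to 17 points of power (pooled) or 12 to 37 (Welch) against log values. At a 20% reduction it loses about 2 points pooled and 8 to 10 Welch. These sizes depend on distributions and effects that the documents do not give. Error rates are sound, and neither the primary analysis nor any claim is affected.

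**What to change.** Add one sentence to Methods: Secondary Aims: hs-CRP and fasting insulin will be analysed as the log of the value at each visit, adjusted for the log of the site visit 1 value, and reported as geometric mean ratios (active/sham) with 95% CI. This also settles, for these two markers, the open questions of scale, change versus follow-up value, and pooled versus Welch. Leave visceral adipose tissue as defined.

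The cost is that sentence, plus results expressed as ratios rather than in original units; the planned descriptive summaries can still show the original units. No new data, visits or subjects are needed.

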Subjects will self-administer VeNS or sham stimulation at home for a total of at least 5 hours a week. If they wish the subjects can use the devices for up to 7 hours a week. The devices are able to detect when they are applied properly, as they measure resistance, and they will record usage data, which they will store pending retrieval when the subjects next attend for review. The skin behind the ears will be visually

inspected during follow up visits and all subjects will be provided with aloe vera gel to apply as required, as this is thought to be particularly effective in preventing skin irritation by VeNS. Subjects will also be advised to contact study staff should they have concerns about skin irritation, and will be provided with contact numbers to do so. If they do then a review will be arranged for when next convenient, and the subject will be advised not to use the device until reviewed. If on review there are ongoing concerns about skin irritation, as evinced for instance by redness, then the subject will be withdrawn from the study.

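### The secondary dose-response model states no usage-by-arm term, so its usage slope cannot separate a response to stimulation from general adherence

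*Combined protocol and SAP*

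**What the plan says.** Section 9, Statistical Considerations, Methods: Secondary Aims, gives both the question and the method in one sentence: the analysts will "investigate the effectiveness of the device by usage by including usage time as a continuous covariate in a linear model for TBWL". The sentence does not say whether group is also in the model, which participants are included, or how usage time is summarised. No usage-by-group term appears anywhere in the document.

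The list of secondary outcome measures adds that "if possible a dose response analysis will also be carried out" and, in the same item, "Analysis will be in an intention to treat manner". Nothing there limits the analysis to the active arm.

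Four other parts of the plan bear on the point:

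- Both arms use a device. Under Device Use Procedure, "Subjects will self-administer VeNS or sham stimulation at home for a total of at least 5 hours a week", with up to 7 hours allowed. Of the devices in general, the plan says "they will record usage data".
- Sham devices deliver no current (Device Use Procedure; Appendix 1).
- Both arms receive the same dietitian sessions and daily app self-monitoring, which the protocol expects to help with weight loss in either arm (Appendix 2).
- No claims are to be made from secondary endpoints (Methods: Secondary Aims).

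**The concern.** Usage is chosen by the participant after randomisation. Someone who wears the device reliably is plausibly also someone who logs meals, follows the dietitian's advice and exercises. That would produce an association between usage and weight loss in both arms, whether or not the current does anything.

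An hour of sham use carries no stimulation, yet a single usage slope counts it the same as an hour of active use. The slope would answer a question about adherence while being described as the effectiveness of the device by usage. The sham arm is the natural control for this, because its slope shows the adherence association without stimulation. The stated model does not use it. At stake is a secondary result that could look like a dose response when none exists, in a study meant to support regulatory submissions.

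**Working it through.** **What there is to reproduce.** The plan gives no power, effect size or alpha for the usage analysis. The check is therefore an illustration at the planned size.

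**Inputs from the plan (Power Calculation).** 60 active and 30 sham participants; SD of TBWL 7.5 percentage points.

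**Assumptions not in the plan.** Two-sided alpha of 0.05 for the usage term; usage standardised, with the same distribution in both arms; a correlation r between usage and TBWL that comes from adherence alone and is equal in both arms; no device effect.

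**Step 1: apparent slope.** With usage in SD units, the slope is r × 7.5. This gives 1.5, 2.25 and 3.0 points of TBWL per SD of usage at r = 0.2, 0.3 and 0.4. Simulated means were 1.50, 2.24 and 2.99.

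**Step 2: how often the usage term is significant.** The approximate noncentrality is r√n / √(1 − r²).

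- r = 0.1, n = 90: 0.1 × 9.487 / 0.995 = 0.95, so about 16%.
- r = 0.2, n = 90: 0.2 × 9.487 / 0.980 = 1.94, so about 49%.
- r = 0.3, n = 90: 0.3 × 9.487 / 0.954 = 2.98, so about 85%.
- r = 0.4, n = 90: 0.4 × 9.487 / 0.917 = 4.14, so about 98%.

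These normal approximations run slightly above the simulated rates, which use the t distribution. The simulation used 4,000 trials per value of r; the r = 0.1 row comes from a separate run of 3,000 trials with group in the model.

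| r in both arms | Usage only | Group + usage | Active arm only | Group-by-usage term |
|---|---|---|---|---|
| 0 | 5.2% | 5.0% | 5.2% | 5.2% |
| 0.1 | not run | 15.4% | not run | 5.3% |
| 0.2 | 48.0% | 47.4% | 33.6% | 4.8% |
| 0.3 | 82.1% | 81.8% | 63.8% | 4.9% |
| 0.4 | 97.8% | 97.8% | 89.6% | 4.4% |

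Adding a group main effect changes almost nothing. Restricting to the active arm lowers the rate only because n falls to 60. The 5% in the last column follows from giving both arms the same slope, so it is a property of the assumption as well as of the model.

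**Step 3: what the interaction can detect.** The standard error of the slope difference is about 7.5 × √[(1 − r_A²)/60 + (1 − r_S²)/30], where A is active and S is sham.

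- r_A = 0.3, r_S = 0: difference 2.25, SE 7.5 × √(0.91/60 + 1/30) = 1.65, ratio 1.36. Power about 28% (simulated 27.8%).
- r_A = 0.5, r_S = 0: difference 3.75, SE 1.61, ratio 2.33. Simulated power 63.3%.
- r_A = 0.4, r_S = 0.2: difference 1.5, SE 1.61, ratio 0.93. Simulated power 15.9%.

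With both correlations near zero, the SE is 7.5 × √(1/60 + 1/30) = 1.68. The 95% interval is then about ±1.96 × 1.68 = ±3.3 points of TBWL per SD of usage.

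**The case against.** **The text is under-specified.** It does not exclude other terms, and the usage covariate may be meant for the TBWL regression described earlier in the section, which includes group. This is fair, and a reader should not infer that the plan fixes usage as the sole predictor. But usage only, group plus usage, and active arm only all leave the confounding in place. The same section also names an interaction where one is wanted: its longitudinal model is specified "with fixed covariates for baseline weight, time, group, and a time / group interaction".

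**The consequence is contained.** The analysis is secondary, conditional on feasibility and covered by the rule that no claims follow from secondary endpoints. This stands and limits the weight of the point. A reader might infer that the plan will present a usage slope as proof of efficacy; the no-claims rule contradicts that. The rule does not, however, remove confounding from the estimate.

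**The correlation is assumed.** This stands. At r = 0.1 the rate is about 15%, and at zero the problem disappears. The one-hour daily lockout limits the spread of usage among compliant participants and could weaken r, although the plan also expects some participants to fall short of 5 hours a week.

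**The interaction is not a clean remedy.** A reader might infer that it restores a 5% error rate. The documents do not support that. Active users may reduce use because of tingling, nausea or disequilibrium (section 14), so adherence slopes could differ between arms with no device effect. If correlations of 0.3 and 0, or 0.4 and 0.2, arose from behaviour alone, the 28% and 16% above would be false-positive rates.

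**Sham logging is not established.** The plan says that devices detect wear through resistance and does not separate active from sham. Comparable logging is plausible but not stated outright.

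**Conclusion.** The point holds as a weakness in one secondary, hypothesis-generating analysis. The stated method has no usage-by-arm term, and none of the three readings tested separates stimulation from adherence. With an inert device and an assumed common correlation of 0.1 to 0.4, the usage term would be significant in about 15% to 98% of trials. These figures illustrate sensitivity to an unknown correlation; they do not predict this trial's result. The slope difference is the better estimate, but it is imprecise at 60:30 and rests on similar adherence slopes and comparable usage logging in the two arms. The primary tests, their power and the sample size do not depend on this analysis. The change is worth making because it is specific and cheap.

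**What to change.** In Methods: Secondary Aims, replace the usage sentence with a prespecified model of TBWL on group, usage and group-by-usage. Report the usage slope in each arm, and define the dose-response estimate as the active slope minus the sham slope, with a confidence interval. State that a pooled or active-only slope will not be interpreted as a device effect. Define the usage measure and how it is handled after dropout.

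State the limits alongside: low power at this size, usage measured after randomisation, and reliance on similar adherence slopes in the two arms. Before the analysis, confirm that sham devices record wear time in the same way as active devices.

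The cost is a few sentences of SAP text and one check of the device logs. No new data collection is needed if sham logging is comparable. The price is a wider interval than a main effect would give.

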- Dietary Counseling from research dietitian including review of diet reports from Healthwatch 360 app – 15 minutes

Summary of Final Site Visit 4 (Final Site Visit) (12 months)

- Urine pregnancy test (if applicable – i.e. a female of child bearing potential)
- Weight and BMI calculation
- Check skin behind ears (visual inspection to ensure appears healthy)
- Waist and hip measurements
- Fasting Insulin level
- High Sensitivity C-Reactive Protein
- Lipid Panel
- Oral Glucose Tolerance Test (OGTT)
- Pulse rate and blood pressure
- Quality of life survey (Duke University IWQOL – <http://www.qualityoflifeconsulting.com/iwqol-lite.html>)
- DXA Scan (whole body scan)
- Coordinator asks participant to complete adverse event monitoring questionnaire.
- Audiogram test including otoscope examination of the ear canals.

Other activities at Visit 4 (12 months):

- The study participant will return the investigational device.

Frequency of Follow-Up Appointments

Visits in person at: enrollment (0 months); 3 months; 6 months; and 1 year. Telephone follow up at: weeks 2; months 1 & 9; and as required on an ad hoc basis. There will also be the facility to bring subjects in for review should concerns be raised after the telephone review – e.g. concern re skin irritation behind the ear. Study participants are also free to contact (call or email) study personnel at any time with any issues or inquiries.

Primary Outcome Measures (At 12 months)

- The difference in mean weight loss between the active-product and placebo-treated groups is at least 5% total body weight lost (TBWL), and the difference is statistically significant.
- The proportion of participants who lose 5% or more of baseline body weight in the active-product group is at least 35% and is approximately double the proportion in the placebo-treated group; the difference between groups is statistically significant.

Secondary Outcome Measures (At 12 months)

- The difference in mean percent loss of baseline total body fat in the active versus placebo treated groups. (As measured by means of a whole body DXA scan– see Appendix 4).
- The proportion of subjects who lose at least 5% of baseline total body fat in the active versus placebo treated groups. (As measured by a whole body DXA scan).
- The difference in mean percent loss of baseline truncal body fat in the active versus placebo treated groups. (As measured by a whole body DXA scan).

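### The planned best-case and worst-case imputations treat both arms alike, so they bound the single-arm 35% test but not the between-arm responder comparison

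*Combined protocol and SAP*

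**What the plan says.** Section 9, Statistical Considerations, Missing Data, plans a sensitivity analysis of the binary endpoint with three parts. The first counts every subject without an outcome as a responder. The second is "a worst-case scenario (assuming no subjects with missing values have lost over 5% body weight". Neither of these scenarios distinguishes active from sham. The third part is given only as "and a tipping point analysis (as described in Yan¹", so its form is left to the cited paper. Beyond these three parts, the section commits to "use multiple imputation techniques to reduce bias in the estimation of the treatment effect".

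The responder endpoint has two tests under Methods: Primary Aims. One concerns the active arm alone: a "one-sided exact binomial test to determine if the response rate in the treatment group significantly exceeds 35" percent. The other is between arms: "We will also use Fisher's exact test to compare the response rates in each group". Under Primary Outcome Measures, the responder criterion requires that the active proportion "is approximately double the proportion in the placebo-treated group; the difference between groups is statistically significant". The Power Calculation section states hypotheses for mean weight loss and for the single-arm responder rate, and says "We will power both of these tests at the 0.025 significance level". It gives no power, alpha or sidedness for Fisher's test.

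**The concern.** A scenario called worst case is normally read as the least favourable result that the missing data allow. For a difference between two arms, that result has missing active subjects failing and missing sham subjects responding. Giving both arms the same outcome moves both rates in the same direction, and with similar dropout in each arm the difference barely changes. The between-group part of the responder outcome could then pass both named scenarios, although neither comes near the limits of what the missing data permit.

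**Working it through.** **Inputs from the plan.** 60 active and 30 sham evaluable subjects, 2:1 allocation, 15% dropout, total recruitment 106, 0.025 for each powered primary test.

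**The plan's own figure.** 90 / 0.85 = 105.9, rounded up to 106. This reproduces.

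**Assumptions.** 106 × 2/3 = 70.7, so 71 active and 35 sham. With 60 and 30 observed, 71 − 60 = 11 and 35 − 30 = 5 are missing (15.5% and 14.3%). Responder counts are hypothetical, because the documents give no sham response rate. Fisher's test is taken as two-sided.

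**Where the extremes lie.** Let *a* and *s* be the observed responders, and *i* (0 to 11) and *j* (0 to 5) the responders among the missing. The difference is

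D(i, j) = (a + i)/71 − (s + j)/35.

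It rises with *i* and falls with *j*, so its minimum is at (0, 5) and its maximum at (11, 0). The plan evaluates (0, 0) and (11, 5), which are neither. The single-arm rate (a + i)/71 depends on *i* only, so for that test the plan's two scenarios are the exact bounds.

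**Illustration: 34/60 (56.7%) vs 7/30 (23.3%), observed difference 33.3 points.**

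| Scenario | Active | Sham | Difference (points) | Fisher p | One-sided binomial p vs 35% |
|---|---|---|---|---|---|
| Plan worst (0, 0) | 34/71 = 47.9% | 7/35 = 20.0% | 27.9 | 0.006 | 0.017 |
| Plan best (11, 5) | 45/71 = 63.4% | 12/35 = 34.3% | 29.1 | 0.007 | <0.001 |
| Arm-opposed worst (0, 5) | 34/71 = 47.9% | 12/35 = 34.3% | 13.6 | 0.22 | 0.017 |
| Arm-opposed best (11, 0) | 45/71 = 63.4% | 7/35 = 20.0% | 43.4 | <0.001 | <0.001 |

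The plan's pair spans 27.9 to 29.1 points. The limits are 13.6 and 43.4. The ratio of rates is 47.9/20.0 = 2.4 in the planned worst case and 47.9/34.3 = 1.4 in the arm-opposed one, against a criterion of roughly two.

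**Lower active rates.** Here the planned worst case fails the 35% test at 0.025, so fragility shows without any change to the plan:

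- 30/60 becomes 30/71, p=0.124.
- 31/60 becomes 31/71, p=0.081.
- 32/60 becomes 32/71, p=0.051.

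Fisher's test alone would not show it. For 30/60 vs 6/30, the planned worst and best cases give p=0.016 and p=0.013, and the arm-opposed worst case (30/71 vs 11/35) gives p=0.30.

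**How common the pattern is for Fisher's test alone.** Assume true rates of 50.8% (the plan's active rate) and 25.4% (half of it, an assumption). Then about 91% of datasets that are significant at two-sided 0.05 under both planned scenarios lose significance at the adverse corner. For 55% vs 25% and 60% vs 30% the figures are 84% and 83%. These shares do not also require passing the 35% test.

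**What a two-arm grid would show.** There are 12 × 6 = 72 combinations of *i* and *j*. For 31/60 vs 7/30, 47 keep p<0.05 and 25 do not.

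**The case against.** A reader might infer that the plan as a whole makes a fragile responder result look robust. The documents do not support that, for three reasons.

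First, the same sentence plans a tipping-point analysis. If it varies the arms separately, it contains the adverse corner and would show the fragility plainly. Its form is deferred to a paper not reproduced in the documents, so they do not settle whether it does.

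Second, the only responder hypothesis written out and powered is the single-arm one, and for that the two scenarios are correct. At active rates near the planned 50.8%, the planned worst case already fails that test. Passing both planned worst-case tests takes a higher observed rate, such as 34/60 = 56.7%.

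Third, the plan never calls the scenarios bounds. It spells out what each imputes, and it ties them to the binary endpoint without naming Fisher's test.

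All three limit the consequence. They do not remove the gap: the between-group difference is part of the primary outcome, no named scenario reaches its extremes, and the tipping-point analysis is not described well enough to be relied on for them. Multiple imputation supplies an estimate under a model, not a bound.

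The arm-opposed corner is also extreme, with no missing active subject and every missing sham subject responding. Failing there does not by itself discredit a result.

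**Conclusion.** The point holds in a limited form. The two scenarios are exact bounds for the test against 35% and are not the extremes of the Fisher comparison. In the illustration, the named scenarios span about 1 point of treatment difference (27.9 to 29.1), while the missing data allow about 30 (13.6 to 43.4), and the p-value moves from 0.006 in the planned worst case to 0.22 at the adverse corner. The conclusion is the same at 0.025 or 0.05.

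The sizes rest on the assumed 71/35 split, 11 and 5 missing, hypothetical responder counts and a two-sided test. The location of the extremes rests on none of the counts, only on some data being missing in each arm. The point concerns sensitivity reporting; the primary tests, sample size and error rate are unaffected. It is a worthwhile improvement, not a serious defect.

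**What to change.** In Missing Data, specify by test:

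- For the single-arm test against 35%, keep the present definitions.
- For Fisher's comparison, worst case: missing active subjects counted as non-responders and missing sham subjects as responders. Best case: the reverse.
- State that the tipping-point grid varies the number of responders among the missing independently in each arm, with these two corners as its limits.

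This should be fixed before unblinding. It costs about one sentence in the plan and two extra tables, with no change to trial conduct. The drawback is that the adverse corner is severe and will look less favourable than the present worst case. It should be labelled as a bound and read alongside the grid, not treated as a hurdle that the result must clear.
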